Clinical Study Protocol: NAV3-21

Study Title: An Evaluation of the Safety of Escalating Doses of Tc 99m Tilmanocept by Intravenous (IV) Injection and Skeletal Joint Imaging with SPECT in Subjects with Active Rheumatoid Arthritis (RA) and Healthy Controls

Study Number: NAV3-21

Study Phase: 1 and 2

Product Name: Technetium Tc 99m tilmanocept

IND Number: 132943

Investigator(s): Multicenter

Sponsor: Navidea Biopharmaceuticals, Inc
[name]

Sponsor Contact: [name]
Associate Clinical Research Project Manager
[contact]

Medical Monitor: [name]
Senior Medical Director
[contact]

Date

Original Protocol: 23 May 2016

Amendment 1: 12 September 2016

Amendment 2: 22 December 2016

Amendment 3: 09 February 2017

Amendment 4: 23 August 2017

Amendment 5: 18 April 2018

Amendment 6: 19 June 2018

Confidentiality Statement

This document and its contents are the property of and confidential to Navidea Biopharmaceuticals. Any unauthorized copying or use of this document is prohibited.

SYNOPSIS

Study title	An Evaluation of the Safety of Escalating Doses of Tc 99m Tilmanocept by Intravenous (IV) Injection and Skeletal Joint Imaging with SPECT in Subjects with Active Rheumatoid Arthritis (RA) and Healthy Controls
Study phase	Phase 1 and 2
Study objective(s)	
Primary
 
Determine the safety and tolerability of escalating doses of Tc 99m tilmanocept. 
Secondary
 
Determine the localization of Tc 99m tilmanocept by SPECT (single photon emission computed tomography) imaging in subjects with active RA and asymptomatic controls and concordance of localization with clinical symptomology.Comparison of localization intensity between Tc 99m tilmanocept dose groups for optimal dose selection and determination of optimal imaging time.To estimate the pharmacokinetics (PK) and dosimetry of Tc 99m tilmanocept in subjects with and without active RA.
Duration of treatment	Up to 53 days
Study drug	Technetium Tc 99m tilmanocept

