 - Assessment of adverse events

	
Post-Tc 99m Tilmanocept Injection Procedures and Follow-Up Visit (Visit 3):
 
 • 18-20 Hours Post Injection: 
 ○ Whole body planar imaging ○ PK blood sampling ○ Vital Signs ○ ECG ○ Physical Exam, including body weight ○ Clinical labs and urinalysis ○ Concomitant medication review ○ Assessment of Adverse Events 	

Planned study dates
	
Start of study recruitment / August 2016
	
End of Recruitment/July 2018 End of Study/September 2018

Planned number of study centers
	
Approximately 1-3 centers in the United States
	

Number of subjects
	
Up to 48 evaluable subjects may be enrolled. The dose escalation portion of this study is a modified 3+3 design with no dose de-escalation. The sequential cohort enrollment characteristics of this design do not allow a fixed computation of sample size. The parameters of the design that can be calculated are shown in Table 4. Based on an assumed vector of probabilities of no subjects experiencing pharmacologic activity or an Adverse Drug Reaction (ADR) in each dose group, the average sample size of the dose escalation phase of the study is n=26.3 patients and the probability that dose group 7 will be selected as the MTD (maximum tolerated dose) is 0.152.
	

Primary endpoint
	
Proportion of subjects not experiencing pharmacologic activity or ADR in each dose group.
	

Secondary endpoints
	
The secondary endpoints for this study are:
 
 • Per subject localization rate of Tc 99m tilmanocept by SPECT imaging • Per joint location clinically RA-identified joint localization rate of Tc 99m tilmanocept by SPECT imaging • Concordance of Tc 99m localization with anatomical areas of active RA defined by clinical symptomology. • Localization intensity for each clinically RA-defined joint (as determined by quantitative SPECT gamma counts) 	

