	
The number and percentage of subjects experiencing pharmacologic activity or ADRs will be tabulated by dose group and overall.
 
Per subject localization rates and percentage will be calculated by time point by dose group and overall.
 
Per joint location localization rates and percentages will be calculated by time point by dose group and overall.
 
Per location concordance of clinical diagnosis to nuclear medicine specialist illumination indication will be computed across all RA positive sites of all subjects at all time points.
 
Localization intensities will be summarized by descriptive statistics (mean, median, standard deviation, minimum, maximum and range) by joint location at each time point.
 
Radiopharmacokinetic (RPK) parameters will be estimated for each subject using noncompartmental models. Summary statistics (n, mean, std, CV, geometric mean) will be computed for each RPK parameter across all subjects by Group (10, 11).
 
For dosimetry data, for each dosimetry parameter, summary statistics (n, mean, std, and a one standard deviation width confidence interval) will be computed by organ type and across all subjects by Group (10,11).

--	--

TABLE OF CONTENTS

SYNOPSIS.....	2
LIST OF IN-TEXT TABLES	13
LIST OF APPENDICES.....	14
LIST OF ABBREVIATIONS AND DEFINITIONS OF TERMS.....	15
STUDY ADMINISTRATIVE STRUCTURE.....	19
1 INTRODUCTION	20
1.1 Background.....	20
1.2 Preliminary Data	23
1.3 Previous Nonclinical Research and Clinical Trial Experience Tilmanocept and Lymphoseek.....	25
1.3.1 Nonclinical Evaluations – Injection Site Subcutaneous	25
1.3.2 Nonclinical Evaluations – IV AND IP Administration	26
1.3.3 Clinical Pharmacokinetics and Pharmacodynamics	29
1.3.4 Clinical Efficacy	29
1.3.5 Clinical Safety.....	30
2 STUDY OBJECTIVES.....	31
2.1 Primary Objective(s).....	31
2.2 Secondary Objective(s).....	31
3 OVERVIEW OF METHODOLOGY AND DESIGN.....	32
3.1 Overall Study Design.....	32
3.2 Justification for Study Design and Population.....	32
3.3 Protocol Adherence.....	33
3.4 Study Duration	33
4 STUDY POPULATION	34
4.1 Eligibility	34
4.1.1 Inclusion Criteria	34
4.1.2 Exclusion Criteria	35
4.2 Recruitment.....	35
4.3 Withdrawal.....	35
4.4 Replacement.....	36
4.5 Subject Identification	36
5 INVESTIGATIONAL PRODUCT.....	37
5.1 Identification of Investigational Product	37
5.2 Investigational Product Dosage and Administration	37
5.3 Treatment Assignment.....	38
5.4 Packaging and Labeling.....	38

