2.2 Secondary Objective(s)

- Determine the localization of Tc 99m tilmanocept by SPECT (single photon emission computed tomography) imaging in subjects with active RA and asymptomatic controls and concordance of localization with clinical symptomology.
- Comparison of localization intensity between the dose groups of Tc 99m tilmanocept by SPECT imaging for optimal dose selection and determination of optimal imaging time.
- To estimate the pharmacokinetics (PK) and dosimetry of Tc 99m tilmanocept in subjects with and without active RA.

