9.3 Efficacy Variables

The efficacy variables for this study are as follows:

- Nuclear medicine specialist qualitative determination of presence/absence of radiotracer uptake (i.e., Tc 99m tilmanocept localization positive/negative) relative to background from SPECT imaging results for each DAS28 joint location for each subject (deemed the “gold standard” result, 28 joint locations per subject)
 - Clinically identified presence/absence of RA using the DAS28 instrument (28 joint locations per subject)
- Quantitative planar imaging intensity of radiotracer uptake for each joint location

A location/joint would be considered clinically identified as RA positive if it is either swollen or tender as measured by the DAS28 instrument. The presence of radiotracer uptake relative to background as determined by the nuclear medicine specialist at a location would indicate the location is RA positive.

The efficacy endpoints for this study are as follows:

- Per subject localization rate of Tc 99m tilmanocept by SPECT imaging
- Per joint location clinically RA-identified joint localization rate of Tc 99m tilmanocept by SPECT imaging

- Concordance of Tc 99m localization with anatomical areas of active RA defined by clinical symptomology.
- Localization intensity for each clinically RA-defined joint (as determined by quantitative SPECT gamma counts)
- Per subject localization rate of Tc 99m tilmanocept in areas other than RA-positive joints by SPECT imaging
- The following PK parameters will be calculated for each subject, whenever possible, using Tc 99m tilmanocept total radioactivity in whole blood and urine: maximum observed concentration (C_{max}), time to C_{max} (t_{max}), area under the concentration-time curve (AUC) from Hour 0 to the last measureable concentration (AUC_{0-t}), AUC extrapolated to infinity ($AUC_{0-\infty}$), apparent terminal elimination rate constant (λ_z), and apparent terminal elimination half-life ($t_{1/2}$).
- Radiation dosimetry of Tc 99m tilmanocept will include radiation doses per organ ($\mu\text{Gy}/\text{MBq}$), organs receiving the highest organ dose (HT), effective doses per organ ($\mu\text{Sv}/\text{MBq}$), mean effective dose ($\mu\text{Sv}/\text{MBq}$), effective dose resulting from a diagnostic dose $\pm 20\%$. Dosimetry will be based on target organ image counts and modeling per OLINDA/EXM® 2.0 software.

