9.5.3 Analysis of Efficacy Variables

Per subject localization rates and percentage will be calculated by imaging time point by dose group and overall.

Per joint location localization rates and percentages will be calculated by time point by dose group and overall.

Per location concordance of clinical diagnosis to nuclear medicine specialist illumination indication will be computed across all RA positive sites of all subjects at all time points.

Localization intensities will be summarized by descriptive statistics (mean, median, standard deviation, minimum, maximum and range) by joint location at each time point.

Other efficacy analyses will be described in the Statistical Analysis Plan (SAP) for the study.

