9.5.4 Analysis of RPK and Dosimetry Variables

The RPK variables for Groups 10 and 11 are the whole blood and urine radioactivity levels per time point. The radioactivity in whole blood will be measured directly using the blood samples. The radioactivity of urine will be obtained from counts of the bladder wall obtained from radiation dosimetry. RPK parameters will be estimated for each subject using noncompartmental models. Summary statistics (n, mean, std, CV, geometric mean) will be computed for each RPK parameter across all subjects by Group (10, 11).

For dosimetry data, for each dosimetry parameter, summary statistics (n, mean, std, and a one standard deviation width confidence interval) will be computed by organ type and overall across all subjects by Group (10, 11). Analysis of Safety Variables

The number and percentage of subjects with any pharmacologic activity or ADRs will be tabulated by dose group and overall.

All adverse events (AEs) will be observed for each subject from the time of signing of informed consent until exit from the study. A treatment emergent adverse event is defined as an adverse event whose start date is on or after the procedure date. If the procedure date and/or the AE start date are missing, the AE will be considered treatment emergent.

Prior to analysis, all adverse events (AEs) will be coded using the MedDRA coding dictionary. Based on these coded terms, treatment emergent AEs will be summarized by dose group and overall as follows:

- by system organ class and preferred terms
- by system organ class and preferred terms and relation to study drug
- by system organ class and preferred terms and severity

Observed and change from baseline vital sign parameters, ECG parameters and hematology, clinical chemistry and urinalysis parameters will be summarized using descriptive statistics (mean, median, standard deviation, minimum, maximum and range) at each time point by dose group and overall.

Other safety analyses will be described in the Statistical Analysis Plan (SAP) for the study.

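### The stated localization-intensity summary has no dose-group split, and joint counts are not scaled for injected activity, decay or scan time, so as written it does not deliver the between-dose comparison in the second secondary objective

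*Combined protocol and SAP*

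**What the plan says.** The objective in Section 2.2 reads "Comparison of localization intensity between the dose groups of Tc 99m tilmanocept by SPECT imaging for optimal dose selection and determination of optimal imaging time". The synopsis says the same.

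The analysis in 9.5.3, repeated in the synopsis under Data Analyses, reads "Localization intensities will be summarized by descriptive statistics (mean, median, standard deviation, minimum, maximum and range) by joint location at each time point". Two sentences earlier, the same section says "Per joint location localization rates and percentages will be calculated by time point by dose group and overall". The safety text at the end of 9.5.4 lists the same statistics and says that they "will be summarized using descriptive statistics (mean, median, standard deviation, minimum, maximum and range) at each time point by dose group and overall".

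The endpoint, in the synopsis and in 9.3, is "Localization intensity for each clinically RA-defined joint (as determined by quantitative SPECT gamma counts". The variable list in 9.3 describes it differently: "Quantitative planar imaging intensity of radiotracer uptake for each joint location".

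Section 8.3 specifies attenuation correction for the whole-body views and for the SPECT slices. Section 8.4 specifies decay correction for blood samples. The protocol states neither decay correction nor scaling by activity or time for joint counts. The background reference in 9.3 belongs to the qualitative positive/negative read, not to intensity.

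Section 9.5.3 closes by leaving other efficacy analyses to an SAP. No separate SAP text is in the document reviewed.

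**The concern.** The objective needs a contrast between dose groups, and the stated table has no dose dimension. The primary efficacy set is the ITD population, which is Groups 1-9 (9.5.1). Read literally, each joint-by-time cell therefore pools all three mass doses and all three radiolabel doses.

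Adding dose group alone would not be enough. If intensity is a raw count, a contrast between radiolabel doses is driven largely by how much activity was injected and how long the camera ran. The contrast between 60 and 180 minutes also contains physical decay. At stake is whether the intensity data can inform dose and imaging-time selection. In addition, in an open-label study, a scaling chosen after the images have been seen leaves that comparison open to data-driven choice.

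**Working it through.** The protocol gives no figure of its own for this point, so there is nothing to reproduce first. The check sets the texts side by side and then does arithmetic on the protocol's inputs.

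**1. Breakdown stated for each analysis**
- Per-subject and per-joint localization rates (9.5.3): time point, dose group, overall.
- Concordance (9.5.3): pooled over subjects and time points.
- Intensity (9.5.3 and synopsis): joint location, time point.
- Vital signs, ECG and laboratory values (9.5.4): time point, dose group, overall.

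Of the efficacy quantities in this list, intensity is the one for which Section 2.2 sets a between-dose comparison, and its sentence omits dose group.

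**2. Injected activity**

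Inputs: 1, 5 and 10 mCi, each ±20% (5.2). Assume equal scan time and equal fractional uptake.
- 10 vs 1 mCi: nominal 10/1 = 10; range 8/1.2 = 6.7 to 12/0.8 = 15.
- 10 vs 5 mCi: nominal 10/5 = 2; range 8/6 = 1.3 to 12/4 = 3.
- Mass-dose contrast within one radiolabel row (for example Groups 1, 2 and 3, all 10 mCi): nominal 1; range 0.8/1.2 = 0.67 to 1.2/0.8 = 1.5.

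**3. Decay between the imaging times**

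Input: half-life 6.02 h (List of Abbreviations). The loss is 1 − exp(−ln 2 × Δt/6.02).
- 60 to 180 min, Δt = 2 h: 1 − 0.794 = 20.6%.
- 75 to 165 min, Δt = 1.5 h: 1 − 0.841 = 15.9%.
- 45 to 195 min, Δt = 2.5 h: 1 − 0.750 = 25.0%.

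**4. Acquisition time**

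Section 8.3 sets a whole-body count target of 5-7 million, anticipates 25-30 minutes, and allows a shorter scan at higher activity. Scan time can therefore vary with activity, so a raw count needs its duration beside it.

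**5. What the data can support once split**

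The expected numbers in Table 4 are 1.6 to 3.5 subjects per group. Summing them over the dose matrix:
- 10 mCi: 3.1 + 3.2 + 3.4 = 9.7
- 5 mCi: 3.5 + 3.3 + 3.2 = 10.0
- 1 mCi: 2.8 + 2.2 + 1.6 = 6.6
- 50 µg: 3.1 + 3.5 + 2.8 = 9.4
- 200 µg: 3.2 + 3.3 + 2.2 = 8.7
- 400 µg: 3.4 + 3.2 + 1.6 = 8.2

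The 95% half-width for a mean is t(0.975, n−1)/√n in SD units: 2.48 at n = 3, 0.92 at n = 7 and 0.72 at n = 10. The pooled summaries are far more informative than the nine-group cells. These widths are best cases, because not every subject will have a given joint clinically positive.

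**The case against.** The strongest reply is the SAP. Section 9.5.3 does not call its descriptive summary the only intensity analysis, and a dose comparison and a count definition could both appear in the SAP before any image is analysed. That stands as a limit on certainty. It does not close the gap: the protocol states the intensity rule itself and does not say that the SAP will add dose groups or scaling.

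Second, intensity is not the only pooled analysis, since concordance is pooled too. This is true, but the objective sets no between-dose comparison for concordance.

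Third, detected signal, including activity and decay, is relevant to choosing a radiolabel dose and an imaging time. This stands, and is why the unnormalised count rate should be reported as well.

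Fourth, the planar and SPECT descriptions of intensity may be terminology only, because the protocol also speaks of planar SPECT scans. That is plausible. Naming the image source is a clarification and does not carry the point.

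Some stronger readings are tempting, and the documents do not support them:
- A reader might infer that the images are uncorrected. Attenuation correction is stated in 8.3.
- A reader might infer that every dose contrast is distorted 10-fold. That applies to the extreme radiolabel rows; mass-dose contrasts within a row share nominal activity.
- A reader might infer that the count target forces scan times to differ about 10-fold between 1 and 10 mCi. The target is a goal, and 8.3 only allows for a shorter scan.

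**Conclusion.** The point holds in limited form. As written, the intensity summary cannot show the between-dose contrast that the objective asks for, and the count measure has no stated scaling for activity, decay or time. The sizes are about 10-fold between the extreme radiolabel doses (6.7 to 15), 0.67 to 1.5 for mass-dose contrasts within a row, and about 21% between imaging times (16% to 25%). All three assume equal scan time; the activity ratios also assume equal fractional uptake, and the decay figure assumes unchanged uptake.

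A reader might infer that dosing within the trial, or the trial's main conclusion, is at risk. The documents do not support that. The primary endpoint is safety (9.2), and Groups 10-11 are dosed at the MTD (5.3), which intensity does not determine. Localization rates by dose group supply some dose evidence. Copies of all images go to the sponsor (8.3), so the table can be rebuilt. The imaging-time half of the objective is partly served already, because the summary is by time point. This should be fixed, but it does not threaten the study.

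**What to change.** In 9.5.3 and the synopsis, have intensities summarized *by dose group and overall, by joint location and time point*. Add pooled summaries by mass dose and by radiolabel dose, because the nine groups are small.

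In 9.3, name one image source and define intensity as count rate, decay-corrected to injection and divided by administered activity. Use assigned activity where measured activity is not recorded. Report the unnormalised count rate as well, so that the signal at each mCi level stays visible. If an SAP already contains these items, a cross-reference from 9.5.3 is enough.

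The cost is wording and a little programming, with no new procedures or subjects. The fix relies on recorded doses and scan times; 8.3 does not say what the image copies contain. If only assigned activity is available, a spread of up to 1.5-fold (1.2/0.8) within a group stays uncorrected. The nine-group table will be sparse: 28 joints × 2 times × 9 groups = 504 cells from about 26 expected subjects. It should be presented as descriptive.

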9.5.4 Analysis of RPK and Dosimetry Variables

The RPK variables for Groups 10 and 11 are the whole blood and urine radioactivity levels per time point. The radioactivity in whole blood will be measured directly using the blood samples. The radioactivity of urine will be obtained from counts of the bladder wall obtained from radiation dosimetry. RPK parameters will be estimated for each subject using noncompartmental models. Summary statistics (n, mean, std, CV, geometric mean) will be computed for each RPK parameter across all subjects by Group (10, 11).

For dosimetry data, for each dosimetry parameter, summary statistics (n, mean, std, and a one standard deviation width confidence interval) will be computed by organ type and overall across all subjects by Group (10, 11). Analysis of Safety Variables

The number and percentage of subjects with any pharmacologic activity or ADRs will be tabulated by dose group and overall.

All adverse events (AEs) will be observed for each subject from the time of signing of informed consent until exit from the study. A treatment emergent adverse event is defined as an adverse event whose start date is on or after the procedure date. If the procedure date and/or the AE start date are missing, the AE will be considered treatment emergent.

Prior to analysis, all adverse events (AEs) will be coded using the MedDRA coding dictionary. Based on these coded terms, treatment emergent AEs will be summarized by dose group and overall as follows:

- by system organ class and preferred terms
- by system organ class and preferred terms and relation to study drug
- by system organ class and preferred terms and severity

Observed and change from baseline vital sign parameters, ECG parameters and hematology, clinical chemistry and urinalysis parameters will be summarized using descriptive statistics (mean, median, standard deviation, minimum, maximum and range) at each time point by dose group and overall.

Other safety analyses will be described in the Statistical Analysis Plan (SAP) for the study.

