3.2 Justification for Study Design and Population

This study is designed to evaluate the safety and tolerability of escalating doses of Tc 99m tilmanocept. Whole body planar as well as a planar scan of the hands using a SPECT camera will also be combined with 3D SPECT or SPECT/CT imaging to provide greater resolution of areas of Tc 99m tilmanocept localization. Additionally, the PK and dosimetry of the MTD of Tc 99m tilmanocept will be evaluated in twelve subjects from Groups 10 and 11. Planar gamma camera imaging will be used to assess dosimetry.

This study is designed to evaluate the use of Tc 99m tilmanocept as an imaging agent in subjects with known active rheumatoid arthritis by evaluating the localization in inflamed joints.

No clinical trials have been conducted to evaluate IV administration of Tc 99m tilmanocept performance in subjects with rheumatoid arthritis. The rationale for evaluating Tc 99m tilmanocept in this subject population is discussed in [Section 1.1](#) and [Section 1.2](#).

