5.2 Investigational Product Dosage and Administration

Subjects will receive the administration of Tc 99m tilmanocept through an intravenous (IV) route of administration. For the 50 and 200 µg doses a single syringe will be used and injected as a slow push into the Y-port. For the 400 µg dose 2 syringes will be used and injected sequentially as a slow push into the Y-port. At the completion of the injection(s), a 10 cc sterile normal saline flush will be administered. Injection volume will be between 0.5 - 4.0 ml in sterile normal saline based on the mass dose group assignment. The preferred site of IV placement will be the left or right antecubital vein unless both elbows are primary sites for RA imaging, and then the site for IV placement will be between the elbow and the wrist.

Tc 99m tilmanocept will be received by subjects through IV administration at one of 3 mass doses: 50 µg, 200 µg, or 400 µg. Within each mass dose group, subjects will receive Tc 99m tilmanocept labeled to one of 3 radiolabel doses: 1 mCi, 5 mCi, or 10 mCi (see Table 1).

Table 1. Dose Escalation Matrix

	Tilmanocept Mass Dose		
Specific Radioactivity Tc 99m	50 µg	200 µg	400 µg
10 mCi	Group 1 n = 3 RA	Group 2 n = 3 RA	Group 3 n = 3 RA
5 mCi	Group 4 n = 3 RA	Group 5 n = 3 RA	Group 6 n = 3 RA
1 mCi	Group 7 n = 3 RA	Group 8 n = 3 RA	Group 9 n = 3 RA

***Group 10 will consist of 6 HC (3 female subjects and 3 male subjects) and Group 11 will consist of 6 subjects (3 female subjects and 3 male subjects) with active RA. Subjects in Groups 10 and 11 will be enrolled in parallel and will be dosed at the MTDs determined from Groups 1-9.**

The final administered dose for groups will be ± 20% of the tilmanocept mass dose and radiolabel mCi dose assignment.

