8 PROCEDURES AND VARIABLES

8.1 Population Characteristics

8.1.1 Demographic and Other Baseline Characteristics

Up to 48 evaluable subjects may be enrolled. Up to thirty-six (36) female or male subjects ≥ 18 years of age with evidence of active RA will be enrolled in Groups 1-9. Three (3) female and three (3) male subjects aged ≥ 18 without evidence of active RA (HC) will be enrolled in Group 10. Three (3) female and three (3) male subjects aged ≥ 18 with evidence of active RA will be enrolled in Group 11.

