9.5 Statistical Analyses

9.5.1 Analysis Populations

The following analysis population will be defined for the study:

- **Intent-to-Diagnose (ITD) Population** - Subjects who are enrolled in the study in Groups 1-9, injected with Tc 99m tilmanocept, and received whole body planar imaging will be included in the ITD analysis population.
- **Radiopharmacokinetic (RPK) Population** – Subjects that have been enrolled in the study in Groups 10-11, injected with Tc 99m tilmanocept, and received whole body planar imaging will be included in the RPK analysis population.
- **Safety Population** – All patients who are enrolled and injected with Tc 99m tilmanocept in the study will be included in the safety population.
- **Per Protocol (PP) Population** – The PP population will include all safety subjects without major protocol violations.

All safety data analyses will be conducted on the safety population. All efficacy data analyses will be conducted on the ITD and PP population with the ITD population being the primary analysis set. All analyses of RPK data will be carried out on the RPK population.

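### The dosimetry interval is set in standard deviation units but called a confidence interval, so it has no stated or constant confidence level for the mean

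*Combined protocol and SAP*

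**What the plan says.** For the dosimetry parameters, Section 9.5.4 lists the number of subjects, the mean, the SD and "a one standard deviation width confidence interval". These are to be tabulated per organ and overall, separately for Groups 10 and 11. The Data Analyses part of the synopsis has almost the same sentence: "summary statistics (n, mean, std, and a one standard deviation width confidence interval) will be computed by organ type and across all subjects by Group". The only difference is that the synopsis omits the word overall. The phrase therefore occurs twice and is not an isolated slip.

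Neither place gives a confidence level, a formula, a standard error or a t quantile. Neither says whether width is the full width or the distance from the mean to one limit. No definition appears elsewhere in the document.

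The interval applies to the organ doses and effective doses listed in Section 9.3, which the synopsis names as secondary endpoints. The planned numbers are small. Section 5.2 says "Group 10 will consist of 6 HC (3 female subjects and 3 male subjects"), and Section 8.1.1 says "Three (3) female and three (3) male subjects aged ≥ 18 with evidence of active RA will be enrolled in Group 11". Section 3.2 gives the total: "the PK and dosimetry of the MTD of Tc 99m tilmanocept will be evaluated in twelve subjects from Groups 10 and 11".

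**The concern.** A confidence interval for a mean has a stated level and a half-width of a t quantile times SD/√n. It narrows as n grows, and under normality its level stays the same. An interval whose width is fixed in SD units behaves in the opposite way: its width stays put and its confidence level moves with n. It describes how much subjects differ, which the SD in the same list already reports.

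Two things are at stake. First, this interval is the only statement of precision planned for the dosimetry means, and a reader judging how well a mean organ dose is known would look to it. Second, the phrase can be programmed in ways that differ twofold in width, each producing output labelled as a confidence interval.

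**Working it through.** The document states no coverage or level for this interval, so there is no figure to reproduce. The check is what coverage the interval would have under each plausible reading.

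**Inputs.** n = 6 in Group 10 (Section 5.2) and n = 6 in Group 11 (Section 8.1.1). n = 5 is included in case one subject yields no usable dosimetry: Section 4.4 replaces only subjects who were not injected or did not proceed to imaging. n = 12 is included only for the case where the two groups are pooled.

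**Formula.** For independent normal observations, the interval mean ± k·SD covers the true mean with probability P(|t(n−1)| < k√n).

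**Readings.**
- Full width one SD (the literal wording): k = 0.5.
- Half-width one SD: k = 1.
- Half-width one standard error (not the literal wording): k = 1/√n, so k√n = 1.

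**Worked at n = 6** (√6 = 2.449, 5 degrees of freedom):
- k = 0.5: P(|t| < 1.225) = 0.725.
- k = 1: P(|t| < 2.449) = 0.942.
- One standard error: P(|t| < 1) = 0.637.

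**Coverage of the true mean, and the half-width a 95% t interval needs:**

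| n | mean ± 0.5 SD | mean ± 1 SD | mean ± 1 SE | 95% t half-width |
|---|---|---|---|---|
| 5 | 67.4% | 91.1% | 62.6% | 1.242 SD |
| 6 | 72.5% | 94.2% | 63.7% | 1.049 SD |
| 12 (only if pooled) | 88.9% | 99.5% | 66.1% | 0.635 SD |

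The last column is t(0.975, n−1)/√n; at n = 6 it is 2.571/2.449 = 1.049. Simulation with 400,000 replicates at n = 6 and n = 12 agreed with the exact coverages to within 0.2 percentage points.

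**Comparison with a 95% t interval at n = 6.** The literal reading has 0.5/1.049 = 48% of the required half-width. Mean ± 1 SD has 1/1.049 = 95% of it, so it is about 5% too narrow.

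**As a description of spread.** At n = 6, mean ± 1 SD contains one new subject's value 60.3% of the time.

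**The case against.** The strongest defence is that the sentence lists summary statistics only. No hypothesis, threshold, group comparison or decision rule uses the interval. With n, mean and SD printed beside it, anyone can build a t interval at any level, so no information is lost and no estimate is biased. At the planned n of 6, mean ± 1 SD is nearly a 95% interval. A one-standard-error interval may also have been meant, and that would be an approximate confidence interval whose coverage drifts little with n.

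Most of this stands, and it limits the severity. It does not rescue the wording. Agreement with 95% under mean ± 1 SD is a coincidence of n = 6: at n = 5 coverage is already 91.1%. The standard-error reading contradicts the text and still lacks a stated level. If the interval is only descriptive, it should not be called a confidence interval.

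A reader might also infer more than the document supports:
- *The interval will be over 50% too wide.* This needs mean ± 1 SD and n = 12 (1/0.635 = 1.57). Results are reported by Group, the word overall can mean across organs within a group, and the synopsis omits it. Pooling is not clearly planned.
- *Readers will be misled into thinking it is a 95% interval.* No 95% level is stated for it.
- *Dose selection is affected.* Under Section 5.3 the dose for Groups 10 and 11 comes from reactions observed in Groups 1 to 9, not from dosimetry.
- *The interval has no coverage at all.* At any fixed n it has a definite coverage; what is missing is a stated level that holds as n changes.

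**Conclusion.** Wrong as written, low severity. The label confidence interval does not fit an interval set in SD units, and the reading to be programmed is undefined. At 6 subjects per group, coverage of the true mean is about 72% on the literal reading, about 94% on the mean ± 1 SD reading and about 64% on the one-standard-error reading. Only the first and third would be materially off if taken as a 95% interval.

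These figures assume independent, normally distributed values and the planned group sizes. I take the dosimetry set to be the one in Section 9.5.1 ("All analyses of RPK data will be carried out on the RPK population"), although that sentence names RPK data only. The consequence is a misdescribed precision for a secondary, descriptive summary. The primary safety result is untouched.

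**What to change.** In Section 9.5.4 and in the synopsis, replace the phrase with a two-sided 95% t confidence interval for the mean, mean ± t(0.975, n−1) × SD/√n, reported by Group next to the n, mean and SD already planned. State whether overall means across organs within a group or across both groups.

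If only between-subject spread was intended, label the quantity mean ± SD and drop the term confidence interval. That resolves the defect equally well.

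The cost is one wording change in two places and one line of programming, with no new data. The text is in the protocol, and Section 3.3 requires a formal amendment for changes that are not solely administrative. The sponsor should decide whether this needs one or can go with the next. The separate statistical analysis plan that Section 9.5 refers to should carry the same definition.
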